7.1.2 PRIMARY SAFETY ENDPOINT

The primary safety endpoint will be the absence of unanticipated serious adverse device effects within 24 hours.

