1.5 Study Purpose

The study is designed to enable the collection, analysis, reporting and presentation of data from use of EmboCube in accordance with the Instructions for Use associated with the product’s CE Mark approval.

The intent of this study is to increase the understanding of the performance of EmboCube in 'real world' patient population, encompassing a broad spectrum of causes of bleeding, treated areas, and patient profiles, to confirm the product's performance and safety in general clinical practice. The intended use of EmboCube includes high-risk anatomical sites and conditions, and so the data collected will be used to amplify knowledge about known or estimated risks, clinical and technical performance, and to identify and evaluate any potential unanticipated adverse device effects, and to integrate that information into product risk analysis and update the clinical evaluation report and labeling, if appropriate.

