8 RISK/BENEFIT ASSESSMENT

8.1 Risks

EmboCube Embolization Gelatin is being used in accordance with the approved CE Mark indication and Instructions for Use.

Vascular embolization is a high-risk procedure. Complications may occur at any time during or after the procedure, and may include, but are not limited to, the following as listed in the device IFU:

- Stroke or cerebral infarction
- Occlusion of vessels in healthy territories
- Vascular rupture
- Neurological deficits
- Infection or hematoma at the injection site
- Allergic reaction, cutaneous irritations
- Transient pain and fever
- Vasospasm
- Death
- Ischemia at an undesirable location, including ischemic stroke, ischemic infarction (including myocardial infarction), and tissue necrosis
- Blindness, hearing loss, loss of smell, and/or paralysis

There are no interactions with concomitant medical treatments identified in the device IFU.

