7.2 SECONDARY OUTCOMES

The secondary outcomes will include the following safety and performance measures:

- Incidence of adverse events (serious and device- and/or procedure-related) to 24 hours post-operative
- Incidence of adverse events (serious and device- and/or procedure-related) between 24 hours and 28 (0/+14) days post-operative

- Technical success defined as successful occlusion of the treated site as seen on post-embolization angiography
- Incidence of device observations related to EmboCube

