8.2 PRIMARY DATA ANALYSES

Endpoints will be analyzed using the ITT analysis set. Additional supportive analyses will be conducted in the PP analysis sets for the primary safety and effectiveness endpoints. All available data will be used for each endpoint and no imputations of data are planned.

The primary endpoint of clinical success (defined as cessation of bleeding post-embolization and absence of re-bleeding at the treated site requiring re-intervention [i.e., repeat embolization or additional surgery], within 24 hours) will be presented as frequency and percentage.

Endpoint Derivation:

- “Was there a re-intervention to treat bleeding?” is checked NO, **AND**
- “Was occlusion of the treated area (as seen on post-embolization angiogram) successful?” is checked YES, **AND**
- “Did subject have any re-interventions post-procedure through 24 hours post-procedure?” is checked NO

The primary safety endpoint of absence of serious adverse device effect within 24 hours will be presented as frequency and percentage

Endpoint Derivation:

- “Did any serious and device- and/or procedure-related adverse events occur during the procedure or up to 24 hours post-procedure?” is checked NO

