8.3 SECONDARY DATA ANALYSES

All secondary endpoints will be tabulated. Means, SDs, and sample size will be used to summarize continuous variables. Distributions of continuous data will be examined and if non-normality is exhibited, medians and interquartile ranges will be presented. Frequencies and percentages will be used to summarize categorical variables. All available data will be used for each endpoint and no imputations will be performed.

Incidence of adverse events to 24 hours post-operative (serious and device- and/or procedure-related)

Endpoint Derivation:

- Serious adverse events as reported by the site, **AND**
- “Seriousness” is checked as anything other than “Not Serious”, **AND**
- Relationship to study device **AND/OR** relationship to study procedure is “Definitely related”

Incidence of adverse events between 24 hours and 28 days post-operative (serious and device- and/or procedure-related)

Endpoint Derivation:

- “Were there any serious and device- or procedure-related adverse events since the 24-hour contact visit?” is checked YES, **AND**
- Serious adverse events as reported by the site and in which “Seriousness” is checked as anything other than “Not Serious”, **AND**
- Relationship to study device **AND/OR** relationship to study procedure is “Definitely related”

Technical success defined as successful occlusion of the treated site as seen on post-embolization angiography

Endpoint Derivation:

- “Was occlusion of the treated area (as seen on post-embolization angiogram) successful?” is checked YES

Incidence of device observations related to EmboCube

Endpoint Derivation:

- “Was procedure aborted due to device observation?” is checked YES

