8.4 SAFETY SUMMARY

All device or procedure-related adverse events collected will be summarized cumulatively throughout the follow-up period. The frequency count of adverse events and the unique number of subjects who had the adverse events will be presented. Also, the frequency and percentage of patients who had a serious adverse event, or a device- or procedure-related serious adverse event will be tabulated separately. If a patient experienced multiple adverse events, only the most severe event or the most intense relationship to the study device will be counted within an adverse event code. The following information will be reported as listings about each adverse event:

- Start date
- Stop date
- Severity
- Relationship
- Action taken
- Outcome

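### No device-only serious event rate, and no unanticipated serious device effect rate, is prespecified to day 28, although the data needed for the device-only rate are collected

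*SAP*

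**What the plan says.** **Purpose.** Protocol 1.5 says the data will be used, among other things, "to identify and evaluate any potential unanticipated adverse device effects", and to feed the risk analysis, clinical evaluation report and labeling.

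**Collection.** Protocol section 7 has serious, potentially device- or procedure-related events documented to 28 days. Protocol 7.4.1 asks for the relationship of each event to device and/or procedure, and SAP 8.3 treats these as two separate items. Protocol section 12 grades relationship as not related, possible, probable or definite.

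**To 24 hours.** SAP 7.1.2: "The primary safety endpoint will be the absence of unanticipated serious adverse device effects within 24 hours." Under SAP 8.2 a subject meets this endpoint when the answer is no to: "Did any serious and device- and/or procedure-related adverse events occur during the procedure or up to 24 hours post-procedure".

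**After 24 hours.** SAP 7.2 has one safety endpoint: "Incidence of adverse events (serious and device- and/or procedure-related) between 24 hours and 28 (0/+14) days post-operative". Its derivation in SAP 8.3 joins the two relationship items with AND/OR and accepts only the definite grade.

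**Safety summary.** SAP 8.4: "All device or procedure-related adverse events collected will be summarized cumulatively throughout the follow-up period." It also says the frequency and percentage of patients with a serious adverse event, "or a device- or procedure-related serious adverse event will be tabulated separately". Each event is listed with its start date and relationship, and SAP 9.2 plans an adverse event listing.

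**Planned tables.** SAP 9.1 names the unanticipated serious device effect only within 24 hours. No table is described as device-only to day 28.

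**The concern.** A post-market study of one device should be able to state how many subjects had a serious event attributed to that device over the period observed. Embolization carries its own procedural complications, so a pooled device-or-procedure count does not answer that question. Protocol 8.1 says complications may arise at any time during or after the procedure and includes infection among those listed, so hour 24 is not a natural end for counting device effects.

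The final report could therefore carry a 24-hour figure labelled as unanticipated device effects that is in fact a pooled count, and a later pooled figure that omits possible and probable events. Anyone updating the risk analysis or labeling would have to build the device rate from listings after seeing the data, with no prior rule on which causality grades count or how to attach an interval.

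**Working it through.** **1. The plan's own figure.** The documents give no precision figure for safety. The only sample-size calculation is for clinical success (SAP 5.5: p = 0.90, limit 0.92 − 0.10 = 0.82, α = 0.05, power 80%). Taking α as one-sided, which is an assumption because the SAP does not say:

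n = (1.645 + 0.842)² × 0.90 × 0.10 / (0.90 − 0.82)² = 86.9, so 87

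87/0.85 gives 103 and 87 × 1.15 gives 101, close to the stated minimum of 100. This says nothing about safety, but it supplies the two sample sizes used below: 100, and 100 × (1 − 0.15) = 85.

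**2. What each planned output isolates.**

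| Output | Period | Device only? | Unanticipated only? | Grades counted |
|---|---|---|---|---|
| Primary safety, as defined (SAP 7.1.2) | 0–24 h | Yes | Yes | Not stated |
| Primary safety, as derived (SAP 8.2) | 0–24 h | No, pooled | No | Not stated |
| Secondary (SAP 8.3) | 0–24 h | No, pooled | No | Definite |
| Secondary (SAP 8.3) | 24 h to day 28 | No, pooled | No | Definite |
| Patient-level table (SAP 8.4) | All follow-up | Unclear | No | Not stated |
| Listings (SAP 8.4, 9.2) | All follow-up | By hand | No | All, as recorded |

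No row prespecifies a device-only rate to day 28, and none identifies unanticipated effects beyond 24 hours. As derived, even the 24-hour endpoint does neither. The text of Protocol 9.2 and SAP 8.2 also drops the word unanticipated, while the SAP 9.1 table titles keep it.

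**3. Why the pooled late endpoint cannot stand in.** Neither document gives an expected number of events, so assume 6 of 100 subjects (6/100 = 6.0%) have a late serious related event.
- If all 6 are procedural only and graded definite, the endpoint shows 6.0% and the device-related rate is 0%.
- If all 6 are device-related and graded possible or probable, the endpoint shows 0% and the device-related rate is 6.0%.

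The planned figure can thus lie above or below the device-related rate and does not bound it.

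**4. What a device-only rate to day 28 would show.** SAP 8.1 already plans Clopper-Pearson 95% intervals. With 0 events the upper limit is 1 − 0.025^(1/n):
- n = 100: 1 − 0.025^(1/100) = 3.6%
- n = 85: 1 − 0.025^(1/85) = 4.2%

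With 1 event the upper limits are 5.4% and 6.4%. The chance of seeing at least one event is 1 − (1 − q)^n, where q is an assumed true rate:

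| q | n = 100 | n = 85 |
|---|---|---|
| 0.5% | 39% | 35% |
| 1% | 63% | 57% |
| 2% | 87% | 82% |
| 3% | 95% | 92% |

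**5. What is already collected.** Relationship to device and to procedure is recorded for each reported event, so the device-only rows need no new data. The report contents in Protocol 7.4.1 include no anticipated/unanticipated field, so that split needs one added classification.

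**The case against.** The study is mainly descriptive, and a 24-hour safety window matches the 24-hour clinical success window. A secondary endpoint covers the rest of follow-up. Unanticipated effects are looked for case by case: events are notified within 24 hours or by the end of the next working day, the sponsor reviews them, and an independent physician adjudicates serious and potentially device-related events (Protocol 7.4.2 and 10.17). Every event is listed with its relationship, and SAP 8.4 counts by strongest relationship to the device within each event code. With about 100 subjects, a late device-related event would be visible.

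Much of this stands, and it rules out several stronger readings that a reader might infer:

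- *Late device effects will be visible only in a pooled count, or the study cannot yield a device rate.* The listings allow a count. The SAP 8.4 wording on separate tabulation may mean all serious events against pooled related ones, or device and procedure apart.
- *The primary safety result will sit near 100% whatever happens.* As derived in SAP 8.2, any serious procedure-related or anticipated event by 24 hours is a failure.
- *Only 27 of 28 days lack a device-specific rate.* As derived, the first day lacks one too.
- *A late necrosis is a clear example of a missed unanticipated effect.* Protocol 8.1 lists "Ischemia at an undesirable location, including ischemic stroke, ischemic infarction (including myocardial infarction), and tissue necrosis" among known complications.

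What the objection does not supply is a prespecified n/N with an interval and a rule for which causality grades count. Case review detects events but does not estimate their rate.

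**Conclusion.** The point holds as a gap in the prespecified analysis, not in data collection or safety surveillance. The plan defines no serious device-related rate and no unanticipated serious device effect rate to day 28. The 24-hour endpoint that claims to isolate such effects is derived from a pooled item, and the later endpoint is pooled and limited to definitely related events.

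The gain from closing the gap is an interpretable device figure: with no events, an exact 95% upper limit of 3.6% (n=100) or 4.2% (n=85). These limits assume the minimum enrollment, and for 85 that the planned 15% loss applies to day-28 safety follow-up. The number of events and their split between device and procedure are not in the documents, so the size of any distortion cannot be estimated; the 6-subject example shows only that it can run in either direction.

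The 24-hour window for the primary endpoint is not itself an error and can stay. The change is worth making because it affects what the study can conclude about the device and costs little.

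**What to change.** 1. In SAP 8.3, 8.4 and the planned tables (9.1), add rows for subjects with (a) a serious device-related event and (b) a serious event related to the procedure only. Give each for 0–24 h, 24 h to day 28, and cumulatively to day 28, as n/N with the exact 95% CI.
2. Build the rows from the separate relationship items and count possible, probable and definite. Splitting the existing SAP 8.3 counts will not do, because they already exclude possible and probable events.
3. Within the device-related rows, show anticipated and unanticipated events, judged against the IFU and Protocol 8.1 list. That list is expressly not exhaustive, so state the reference list before the analysis.
4. Reconcile the SAP 8.2 derivation, and the wording there and in Protocol 9.2, with the endpoint in SAP 7.1.2, so that the 24-hour row is also device-specific.
5. State in SAP 8.4 whether separate tabulation means device and procedure apart.

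**Cost:** SAP wording, a few table rows, and one anticipated/unanticipated classification per serious device-related event, since Protocol 7.4.1 lists no such field. The sponsor already reviews each event. No change to visits or follow-up is needed.

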7.2 SECONDARY OUTCOMES

The secondary outcomes will include the following safety and performance measures:

- Incidence of adverse events (serious and device- and/or procedure-related) to 24 hours post-operative
- Incidence of adverse events (serious and device- and/or procedure-related) between 24 hours and 28 (0/+14) days post-operative

- Technical success defined as successful occlusion of the treated site as seen on post-embolization angiography
- Incidence of device observations related to EmboCube

7.3 DEMOGRAPHY AND BASELINE CHARACTERISTICS

The following demographic and baseline data for study subjects will be collected and reported:

- Demographic information (age at time of treatment/enrollment, sex, and ethnicity [if permitted by local regulations])
- Relevant medical history
- Diagnosis (i.e., cause and location of bleeding or hemorrhage)
- Height, weight, body mass index
- Concomitant anticoagulants and antiplatelet medications

Data collected for the embolization procedure with EmboCube will also be reported.

7.4 SUBJECT DISPOSITION

A tabulation of study subject disposition will be presented including the number of subjects treated and the number of subjects that do not complete the study, the reasons for study incompleteness will be described as documented in the case report form.

8 STATISTICAL METHODOLOGY

8.1 GENERAL METHODOLOGY

Final analyses will be performed after all study subjects have completed the final follow-up visit, defined according to the protocol as 28 (0/+14) days.

For continuous variables, outputs will be presented with mean, standard deviation (SD), median, minimum, and maximum values. Mean and median values will be rounded to a single decimal place while SD will be rounded to two decimal places. When appropriate, a corresponding 95% confidence interval (CI) will be calculated. Categorical variables (e.g., sex, race) will be reported using frequencies and percentages. All percentages will be rounded to one decimal place. If percentages do not add up to 100% due to rounding, a footnote explanation will be provided accordingly.

When the mean is not an appropriate measure of central tendency, alternative statistics will be considered (e.g., median). When the distribution of a variable does not support the use of parametric statistics, nonparametric approaches or data transformations may be implemented. If data transformations are used, they will be specified in the final clinical report.

Correlation analyses will be used to analyze relationships for continuous variables. Independent t-tests will be conducted to test differences for continuous variables between binary groups. A Fisher's exact test will be used to analyze the relationships between categorical variables. P-values less than or equal to 0.05 will be considered significant. All p-values will be rounded to 3 decimal places and will be presented as "<0.001" if less than 0.0005.

Time-dependent response variables will be expressed using the Kaplan-Meier curve, and the hazard ratio and the 95% CI will be reported.

Data for all categorical endpoints are shown with the number of patients, percentage, and Clopper-Pearson's exact 95% CI.

Descriptive statistics will be used to examine demographic and baseline characteristics and to perform other efficacy analyses.

Each table generated will have headers that include the total sample size (N). Frequencies and percentages for categorical variables will be calculated using the number of subjects (n) with non-missing values.

8.1.1 DATA SOURCE

All data will be extracted from Medrio, which is the electronic data capture (EDC) used for data collection in this study. Datasets will be merged and cleaned prior to data analysis. Data processing procedures will be documented to ensure replicability and support error checks. All analyses and codes will be uploaded to Merit Medical Affairs Share (SharePoint) drive.

8.1.2 REPORTING OUTPUTS

SAS software Version 9.4 (SAS Institute Inc., Cary, NC, USA), or other widely accepted statistical or graphical software as required, will be used for all statistical analyses and in the generation of exhibits. Tables will be formatted using SAS software and Microsoft Office.

8.1.3 HANDLING OF MISSING DATA

No imputation of missing data is planned.

8.1.4 CLASSIFICATION OF PROTOCOL VIOLATION

Protocol deviations will be summarized in the final clinical study report. For reporting purposes, the Sponsor classifies the following as major protocol deviations:

- Any deviation from subject inclusion and exclusion criteria
- Failure to obtain subject informed consent
- Failure to report serious adverse events

Other deviations that occur will be reviewed and classified by the Sponsor.

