7.4.2 Reporting Requirements for Serious Adverse Events

All serious and potentially device and/or procedure-related adverse events, and all deaths must be reported to the Sponsor within 24 hours of knowledge of the event or by the end of the next working day. This may be done via eCRF or by phone, fax, or email using the contact details provided separately to sites.

The Sponsor will review all reported events for potential reporting in accordance the requirements of Regulation (EU)2017/745 of the European Parliament and of the Council of 5 April 2017 on Medical Devices (MDR), and any applicable guidance(s). Sponsor may request medical record documentation (e.g., procedure notes, operative notes, discharge summary, relevant progress notes, imaging, or lab studies) to facilitate this review.

The Sponsor will determine whether all of the local Investigators need to be informed immediately of an SAE, or whether this can be postponed until the next regularly scheduled study update.

The Sponsor will ensure reporting of applicable events to Regulatory Authorities as clinical study safety reports, if required by Local/national regulations.

The Investigator is responsible for reporting applicable serious adverse events to their EC/IRB as required by EC/IRB procedures and local/national regulations. A copy of each EC/IRB safety report will be provided to Sponsor.

Local, specific safety reporting will be specified in a separate safety plan.

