10.15 Protocol Compliance/ Deviations

The Investigators are responsible for ensuring that this study is conducted according to this Protocol.

All deviations from the Protocol must be reported to the Sponsor.

Investigators shall be required to obtain prior approval from the Sponsor before initiating deviations from the Protocol, except where necessary to protect the life or physical well-being of a subject in an emergency. Such approval shall be documented in writing and maintained in Sponsor and Investigator files.

Investigators will also adhere to procedures for reporting Protocol deviations to their EC/IRB in accordance with their specific EC/IRB reporting policies and procedures.

For reporting purposes, the Sponsor classifies the following as major protocol deviations: Any deviation from subject inclusion and exclusion criteria, failure to obtain subject informed consent and failure to report serious adverse events. Other deviations which occur will be reviewed and classified by Sponsor.

The Sponsor shall report deviations from the approved protocol in the study report.

If the Sponsor and/or their authorized representative become aware that an Investigator is not complying with the study protocol, the Investigator Agreement, the Declaration of Helsinki, applicable privacy standards, or any condition of the study imposed by the IRB / EC, the Sponsor or their authorized representative may immediately secure compliance or suspend or terminate enrollment at site. An inability to secure compliance and/or to complete an investigation into the factors that are inhibiting compliance may result in the Investigator's termination from the study by the Sponsor.

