6 ANALYSIS POPULATION

The following analysis populations are identified for the study:

- Intention-to-Treat (ITT) analysis set: includes all enrolled subjects.
- Per-Protocol (PP) analysis set: includes all enrolled subjects who meet all inclusion/exclusion criteria with no major protocol deviations. This is a secondary analysis set for the primary safety and effectiveness endpoints, as well as secondary endpoints.

While the ITT analysis set is intended as the primary analysis set for all safety and effectiveness endpoints, the primary safety and effectiveness endpoints will also be evaluated in the PP analysis set as supportive information. All subjects excluded from the ITT analysis set will be described.

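### An unreported serious adverse event counts as a major deviation and so removes the subject from the per-protocol set, which makes per-protocol membership depend on a post-treatment outcome

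*SAP*

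**What the plan says.** Two rules have to be read together.

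- **Who is in PP.** Under SAP 6 the PP set "includes all enrolled subjects who meet all inclusion/exclusion criteria with no major protocol deviations". The analysis-population text in protocol section 9 agrees.
- **What is major.** SAP 8.1.4 opens its list with "For reporting purposes, the Sponsor classifies the following as major protocol deviations" and names three items: departures from the eligibility criteria, lack of informed consent, and "Failure to report serious adverse events". Protocol 10.15 has the same list, ending with "failure to obtain subject informed consent and failure to report serious adverse events". Any other deviation is left to the sponsor to classify.

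Neither document exempts the reporting item when PP is built, and neither gives a separate meaning of major for that purpose.

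The reporting duty is in protocol 7.4.2: "All serious and potentially device and/or procedure-related adverse events, and all deaths must be reported to the Sponsor within 24 hours of knowledge", or by the end of the next working day. Reportable events are collected to 28 days (protocol 7 and 7.4.1).

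PP results are planned output. SAP 8.2 says "Additional supportive analyses will be conducted in the PP analysis sets for the primary safety and effectiveness endpoints", and SAP 6 says of PP: "This is a secondary analysis set for the primary safety and effectiveness endpoints, as well as secondary endpoints". SAP 9.1 lists PP tables for the primary endpoints and for the secondary endpoints, including adverse-event incidence. ITT is the primary set throughout.

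**The concern.** A per-protocol set should be formed by criteria that do not depend on the result being analysed. Eligibility and consent meet that test. The third item does not, because a subject without a reportable serious event can never trigger it. It records a fault in the site's reporting and says nothing about whether the subject was eligible or treated as intended.

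The trigger also overlaps with what is measured. The SAP 8.2 derivation of the primary safety endpoint asks whether any serious event related to the device or procedure occurred up to 24 hours. Within that window, those are largely the events that sites must report. If monitoring or data review finds one that was not reported, ITT counts the subject as a failure and PP removes the subject.

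Effectiveness can be affected too. Protocol 7.1 includes in its definition of a serious event a medical or surgical intervention to prevent life-threatening illness. Rebleeding that needs re-intervention can meet that definition and also fails clinical success.

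At stake is whether the PP tables can do their supportive job for safety. Agreement between PP and ITT carries less weight if one of the PP exclusions is triggered by having had an event.

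**Working it through.** **The plan's own figure.** The documents give no number for this rule. The only figure used here is the planned N of 100, as a denominator. It reproduces approximately from the SAP 5.5 inputs, taking alpha as one-sided and the variance at p = 0.90. The null is 0.92 − 0.10 = 0.82, so

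n = 0.90 × 0.10 × (1.645 + 0.842)² / (0.90 − 0.82)² = 86.94, rounded up to 87.

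Allowing for 15% loss gives 87/0.85 = 102.4 (103), or 87 × 1.15 = 100.05 (101).

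**Formula for the rule.** Let E be the subjects with an endpoint event among N. Let u be the event subjects excluded for a reporting failure. Let v be the subjects excluded for a reporting failure on an event that is not an endpoint event.

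- ITT rate = E/N
- PP rate = (E − u)/(N − u − v)

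**Inputs.** The documents give neither a serious-event rate nor a non-reporting rate. E, u and v are therefore assumptions, shown over a range with N = 100.

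| E | u | v | ITT rate | PP rate |
|---|---|---|---|---|
| 2 | 1 | 0 | 2.0% | 1/99 = 1.0% |
| 5 | 1 | 0 | 5.0% | 4/99 = 4.0% |
| 5 | 2 | 0 | 5.0% | 3/98 = 3.1% |
| 10 | 1 | 0 | 10.0% | 9/99 = 9.1% |
| 10 | 5 | 0 | 10.0% | 5/95 = 5.3% |
| 20 | 5 | 0 | 20.0% | 15/95 = 15.8% |
| 5 | 0 | 1 | 5.0% | 5/99 = 5.05% |
| 5 | 0 | 5 | 5.0% | 5/95 = 5.3% |

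**Direction on the reported scale.** The primary safety endpoint is "absence of unanticipated serious adverse device effects within 24 hours", so the percentage shown is event-free subjects. With E = 5 and v = 0 it rises from 95.0% to 96.0% for u = 1 and to 96.9% for u = 2.

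**Which direction dominates.** The PP rate is below the ITT rate when u(N − E) > vE. At E = 5, one exclusion with an endpoint event is offset exactly by 95/5 = 19 exclusions without one: 4/(100 − 1 − 19) = 4/80 = 5.0%. The two effects per subject are thus very unequal, but if u = 0 the rate can only rise.

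**Scale against sampling error.** The exact 95% interval is 1.6% to 11.3% for 5/100 and 0.6% to 8.7% for 3/98. The shift is visible in the point estimate and small beside the interval width.

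**Clinical success.** At the planned 90%, excluding two failures gives 90/98 = 91.8%.

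**The case against.** Four counter-arguments deserve weight.

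- **The list is for reporting only.** Both lists are introduced as being for reporting purposes, and protocol 10.16 treats failure to comply with safety reporting as a ground for closing a site. A narrower reading is therefore possible, in which the item was never meant to shape PP. This stands in part. However, a programmer building PP has no other definition of major to use, so the intention has to be written down.
- **The direction is not fixed.** A reader might infer that PP safety is always made to look better. The documents do not support that. Reporting runs to 28 days while the primary safety endpoint stops at 24 hours. All deaths are reportable whatever their cause. The secondary adverse-event derivations in SAP 8.3 count only events rated as definitely related, whereas potentially related events are reportable. The endpoint as worded in SAP 7.1.2 is also narrower than its derivation in SAP 8.2. Excluding a subject whose event falls outside the endpoint raises the PP rate a little. This objection stands.
- **The rule may seldom operate.** It needs a reporting failure that is later found, because an event never found is missing from ITT and PP alike. Remote review and queries (protocol 10.8 and 10.12) should limit such failures. The documents do not say whether a late report counts as a failure to report; if it does, exclusions would be more frequent. The frequency is unknown.
- **PP is only supportive.** ITT is primary, no decision rule rests on PP, and a deviations table and listing are planned, so a reader could trace the exclusions. This stands and limits the consequence.

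**Conclusion.** The point holds in a limited form. As written, the two rules let a post-treatment outcome decide PP membership, in analyses that include the primary safety endpoint. When the excluded subject had an endpoint event, PP looks safer than ITT: about 1 percentage point for one exclusion among 5 events in 100, and about 2 points for two. When the excluded event is not an endpoint event, the shift is about 0.05 points the other way. These sizes rest on assumed counts and on the failure being discovered later.

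Two stronger conclusions do not follow. A reader might infer that the primary result is compromised, but the rule does not touch ITT. A reader might also infer that PP could show no events at all. That would require every subject with an endpoint event to have a reporting failure, and nothing in the documents suggests it.

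**What to change.** Add one sentence to SAP 6, with the same wording in the PP definition of protocol section 9: *failure to report a serious adverse event remains a major deviation for reporting but does not by itself exclude a subject from the PP set*. Both documents need it; changing the SAP alone would leave two different PP definitions.

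The lists in SAP 8.1.4 and protocol 10.15 can stay as they are, and no further PP criterion needs to be added. The sentence also means that, for PP, it no longer matters whether a late report counts as a failure to report.

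The cost is one sentence in each document, with the protocol change handled under protocol 10.14. No new data are needed, N does not change, and the ITT analyses are unaffected.
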